## **Post Treatment Procedures**

1. Safety aspect will be assessed before and after each treatment:
  - a. Clinical effects - All visible and palpable immediate response will be recorded for the entire treatment area using a 4-point severity scale (Table 4)
  - b. Adverse Events – Record the number, severity and type of any adverse event occurred before, through and after treatments.

## **Return Visits**

All subjects will be requested to return to the clinic at the following time-points during the study in order to assess the clinical performance of the device:

- Visit 4: FU1 – 4 weeks ( $\pm 7$  days) post last treatment.
- Visit 5: FU2 – 8 weeks ( $\pm 7$  days) post last treatment.
- Visit 6: FU3 – 12 weeks ( $\pm 7$  days) post last treatment.

At each return visit the following procedures will be conducted and data recorded:

- Weight.
- Ultrasound fat-thickness measurements.
- Caliper fat-thickness measurements.
- Circumference measurements.
- Skin assessment for clinical effects due the procedures:
  - Post treatment response and adverse events.
- Photographs as conducted at baseline.
- Satisfaction questionnaire performed by the investigator using the Global Aesthetic Improvement (GAI).
- Completion of the Subject Follow Up questionnaire:
  - Subjective Improvement and satisfaction performed by the subject using the Global Aesthetic Improvement (GAI).
- At the final visit a urine pregnancy test will be performed for women with childbearing potential.

 Syneron Medical Ltd. Confidential	Clinical Study to Evaluate the Safety and Efficacy of the SlimShape Device for Abdominal Fat and Circumference Reduction			
	Protocol #	DHF22621	Rev. Date	October 8, 2017

## **DATA ANALYSIS**

### **Recording**

All data will be recorded on site source documents and transcribed onto Case Report Forms (CRFs). The site will be monitored by Syneron staff or designees to assure adherence to the clinical trial requirements, subject safety, protocol procedures, and for data accuracy. The Case Report Forms and images will be reviewed and retrieved during the monitoring visit. All source documentation will remain in the subject's files at the site.

Review and Analysis of all data collected will be conducted by the Sponsor or designee as described for this protocol with the following data:

### **Demography and Baseline Measurements**

Demographic and baseline/screening measurements (e.g., weight, height and digital images) will be collected and descriptively presented.

### **Treatment Visit**

Skin assessment by the PI, photographs of the treated region, and pain scores will be collected used to document any adverse events to assess the device performance.

### **Follow-up Visit Measurements**

Follow-up measurements for weight, circumference and digital images will be used for comparative measurements with their respective measurement at baseline. Primary endpoints will be evaluated 12 weeks post last treatment. Secondary endpoints may be evaluated at all visits.

### **Safety**

Safety of device procedure will be evaluated through skin assessments by the PI and research staff. The occurrence and severity of all complications from the start of the study will be recorded.

### **Protocol Revisions and/or Deviations**

With the exception of emergency situations, no changes or deviations in the conduct of this protocol will be permitted without the prior approval of the sponsor.

The IRB/IEC that granted original approval for the study must be notified of all changes in the protocol, and will approve any change or deviation that may increase risk to the subject, and/or that may adversely affect the rights of the subject or validity of the investigation.

 Syneron Medical Ltd. Confidential	Clinical Study to Evaluate the Safety and Efficacy of the SlimShape Device for Abdominal Fat and Circumference Reduction			
	Protocol #	DHF22621	Rev. Date	October 8, 2017

In the event of an emergency, the Investigator will institute any medical procedures deemed appropriate. However, all such procedures must be promptly reported to the sponsor and the IRB/IEC.

## **ADVERSE EVENTS (AE)**

An adverse event (AE) is any adverse change in health or side effect that occurs in a study participant during their participation in the study.

### **Anticipated Adverse Effects**

Following treatment with the *SlimShape* the following local adverse effects could occur (anticipated):

- Purpura
- Blister
- Bruising
- Bullae
- Erosion
- Pain/ soreness
- First degree burn
- Second degree burn

An adverse event (AE) is any undesired clinical occurrence in a study subject as indicated by signs, symptoms, illnesses, events that develop or worsen in severity in association with the study when deemed by the Investigator to be related to use of the device or study procedures. The Investigator will document all adverse signs and symptoms regardless of severity or frequency that are either volunteered by subjects or observed during the course of the study that are related to the device. The Investigator will also record adverse experiences of subjects resulting from concurrent illnesses, reactions to concurrent medications, or progression of disease states that the Investigator deems related to the device. Included in the description will be the nature of the sign or symptom, the date of onset, whether the event was serious, the severity, the relationship to study procedures or investigational device, the action taken, the date of resolution, and the outcome. The Principal Investigator will determine the relationship of the adverse device effect to the investigational device.

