**Table 2 – Clinical Evaluation Measurements and Tools**

Measurement	When to conduct	Method
Height	Baseline	Scale
Weight	Prior to all treatments (Tx.1, Tx.2 & Tx.3), and at all follow-ups visits (4wk FU, 8wk FU & 12wk FU)	Scale
BMI		Calculation
Fat thickness UltraSound measurements	Baseline, Prior to Tx.3, and at all follow-ups visits (4wk FU, 8wk FU & 12wk FU)	Ultrasound device
Fat thickness Caliper measurements	Prior to all treatments (Tx.1, Tx.2 & Tx.3), and at all follow-ups visits (4wk FU, 8wk FU & 12wk FU).	Calibrated Caliper
Circumference measurements		Standardized circumference measuring tape
Photographs		Standardized digital photographs
Urine pregnancy test	Prior to all treatments (Tx.1, Tx.2 & Tx.3), and at the last follow-up visit (12wk FU)	Urine pregnancy test
Immediate response assessment	Immediately after each treatment (Tx.1, Tx.2 & Tx.3)	Post Treatment Side Effect Severity Scale (Table 4)
Investigator satisfaction	At all follow-up visits (4wk FU, 8wk FU and 12wk FU)	Satisfaction Questionnaire (Table 6)
Subject satisfaction		Satisfaction Questionnaire (Table 6)
Subject improvement assessment		Improvement Questionnaire (Table 5)
Safety	During treatment and throughout study.	Examination of skin in the treated area, interview subjects, Adverse Events form, Occurrence and Severity Ratings, as well as relation to treatment, action taken and outcome

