**The relationship of the adverse effect to the study is defined as follows:**

**Probable:** An adverse event has a strong temporal relationship to study device, and another etiology is unlikely or significantly less likely.

**Possible:** An adverse event has a strong temporal relationship to the study device, and an alternative etiology is equally or less likely compared to the potential relationship to study device.

**Probably not:** An adverse event has little or no temporal relationship to the study device and/or a more likely alternative etiology exists.

**Not related:** An adverse event has no temporal relationship to study device or has a much more likely alternative etiology.

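### The protocol defines adverse event twice, once without regard to cause and once only for events the investigator judges related, and does not say which definition governs

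*Combined protocol and SAP*

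**What the plan says.** The protocol defines the term in two neighbouring sections.

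- **Adverse Events (AE), opening sentence:** "An adverse event (AE) is any adverse change in health or side effect that occurs in a study participant" while taking part. There is no condition on cause.
- **Anticipated Adverse Effects:** after a list of expected local effects, a second definition uses the same term and abbreviation. It covers undesired occurrences that develop or worsen "in association with the study when deemed by the Investigator to be related to use of the device or study procedures".
- **Same section, recording:** one sentence asks for signs and symptoms that subjects volunteer or that are "observed during the course of the study that are related to the device". The next asks for experiences arising from concurrent illness, reactions to other medication, or "progression of disease states that the Investigator deems related to the device".
- **Same section, attribution:** "The Principal Investigator will determine the relationship of the adverse device effect to the investigational device".

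The safety endpoint, in the synopsis and under Primary Safety Endpoint, is how many adverse events are recorded during the study, how severe they are and of what type. It carries no relatedness condition.

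Two further places treat relatedness as something noted about an event after it has been recorded. The Safety row of Table 2 lists "Occurrence and Severity Ratings, as well as relation to treatment, action taken and outcome". The relationship scale has four levels, and its third level (Probably not) reads "An adverse event has little or no temporal relationship to the study device and/or a more likely alternative etiology exists".

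No section says which definition takes precedence, or that the second is meant as a subset of the first.

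**The concern.** For an event the investigator judges unrelated, the two definitions give opposite answers. The difference reaches recording as well as vocabulary, because the second definition is followed by instructions on what to document and those instructions carry the same kind of filter.

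The number at stake is the primary safety endpoint. If some sites record every adverse change and others only what they attribute to the device, the pooled count mixes two quantities. The study has one arm and no concurrent control, so relatedness rests on the investigator's opinion. An event screened out before it reaches the form leaves nothing for the sponsor or a later reader to reassess.

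**Working it through.** No arithmetic in the plan depends on this point, so the check compares the texts.

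**Step 1. Apply each text to the three possible judgements.**

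| Investigator's judgement | Opening definition | Second definition | Recording sentences after it |
|---|---|---|---|
| Related to the device | AE | AE | To be recorded |
| Related to a study procedure, not to the device | AE | AE | Not named |
| Related to neither | AE | Not an AE | Not named |

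The last row is the contradiction between the two sections. The middle row is a smaller one inside Anticipated Adverse Effects: its definition takes in study procedures, but its recording sentences name only the device.

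**Step 2. Count the conditions.** Anticipated Adverse Effects has 1 in the definition + 2 in the recording sentences = 3 relatedness conditions. The opening definition has 0. This shows that the restriction is repeated and is not a single slip. It does not measure any effect on the data.

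**Step 3. See which definition the rest of the safety text fits.**

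- *Relationship scale:* 2 of its 4 levels, Probably not and Not related, describe events more likely due to something else, and both speak of an adverse event. Under the second definition most such events would never reach the scale.
- *Table 2, Safety row:* it runs through the whole study, calls for interviewing subjects and an adverse event form, and records relation to treatment as an attribute.
- *Post Treatment Procedures:* it asks for any adverse event before, during and after treatments, with no causal filter of its own. An event before the first treatment cannot be a device effect.
- *Table 3 (Appendix I):* Safety Monitoring is a separate row, marked at 3 treatment visits + 3 follow-up visits = 6 visits.

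These lean to the broad definition. None states that it overrides the second, and those that use the term adverse event inherit its ambiguity.

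**Step 4. Write down the loss.** At a site s that applies the second definition, let U_s be the events judged unrelated to device and procedures, and P_s the events judged related only to a procedure.

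- Following the definition: loss = sum of U_s over those sites.
- Following the recording sentences literally: loss = sum of (U_s + P_s) over those sites.
- Events attributed to the device: loss = 0 under either reading.

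The documents give no value for U_s or P_s, and the number of such sites could lie anywhere from 0 to 10. The loss is zero if every site uses the opening definition and otherwise cannot be computed.

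**The case against.** The strongest reply is that the second definition is a paragraph on adverse device effects carrying the wrong label. It sits under a heading about anticipated effects, its last sentence speaks of the adverse device effect, and the glossary lists ADE separately from AE. The sentence before that makes relationship to procedures or device a recorded attribute. On this view a sensible site records everything and classifies afterwards, and a site that does so also meets the narrower recording sentences.

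This is a plausible account of what was intended, and it limits the consequence, but it does not remove the conflict. The text defines adverse event, not adverse device effect. It reaches concurrent illness, medication reactions and disease progression, which are not the listed local effects. Nothing else tells a site to record unrelated events under another name.

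The reply is right on the balance of the document: the remaining safety text mostly favours the broad definition. A reader might infer from Return Visits, where adverse events are listed under "Skin assessment for clinical effects due the procedures", that follow-up visits collect only procedure effects. The documents do not support that. Table 2 requires interviews and an adverse event form throughout, and Table 3 schedules Safety Monitoring at every visit.

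The reporting section also asks for unanticipated adverse events with no relatedness test of its own. Because it uses the disputed term, it settles nothing.

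**Conclusion.** The inconsistency is real and should be fixed. Two definitions of one term disagree on events judged unrelated, no precedence is stated, and the primary safety endpoint depends on the answer. The consequence is conditional: it arises only at sites that apply the second definition, and its size cannot be computed from the documents.

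Two stronger readings do not hold. A reader might infer that device-related harm would go unrecorded, but events attributed to the device are captured under both definitions. What is lost is the chance to revisit an attribution. Even that loss may be partial, since monitors have direct access to source documents and could find events that were charted, though not those never written down.

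A reader might also infer that severity has the same fault because Severe appears both in the grading of unanticipated effects and in Table 4. Only the former defines the word. Table 4 gives a bare label, and it serves the immediate and expected treatment responses, so the two scales grade different things.

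**What to change.** 1. Use the opening definition of adverse event throughout.
2. In Anticipated Adverse Effects, delete the relatedness condition from the definition and from both recording sentences. Alternatively, relabel that definition as adverse device effect, say that it is a subset of adverse events, and state that all adverse events are still recorded.
3. Assign relationship after recording, with the existing four-level scale.
4. Report all adverse events and device-related adverse events side by side.

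The cost is a wording change with IRB/IEC notification, which Protocol Revisions and/or Deviations requires for every protocol change, at up to 10 sites. There will be additional entries on the adverse event form already in use; how many cannot be said without an event rate. The total adverse event count will be higher and will include events unrelated to the device. Reporting both counts keeps that total interpretable.

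### Table 2 requires subjects to be interviewed about adverse events, but the recording rule, the follow-up visit list and the safety analysis do not mention it, and the plan never reconciles them

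*Combined protocol and SAP*

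**What the plan says.** The places that bear on how an adverse event is found and recorded are these.

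- **Table 2, Safety row.** The method is "Examination of skin in the treated area, interview subjects, Adverse Events form, Occurrence and Severity Ratings" and the timing is "During treatment and throughout study". The Enrollment and Screening section introduces the table as measurements that are to be carried out, so the interview is mandatory.
- **Anticipated Adverse Effects.** The investigator's rule for documenting signs and symptoms is "regardless of severity or frequency that are either volunteered by subjects or observed during the course of the study"; the sentence then limits this to device-related ones. The next sentence adds: "The Investigator will also record adverse experiences of subjects resulting from concurrent illnesses, reactions to concurrent medications, or progression of disease states", where these are judged device-related. That sentence carries no volunteered-or-observed condition. The section also asks for dates of onset and resolution and for the outcome.
- **Return Visits.** The item is "Skin assessment for clinical effects due the procedures", with post-treatment response and adverse events nested beneath it. No interview is listed. The subject questionnaire named there covers improvement and satisfaction.
- **Data Analysis, Safety.** "Safety of device procedure will be evaluated through skin assessments by the PI and research staff". The sentence after it asks that all complications since study start be recorded.
- **Post Treatment Procedures.** "Record the number, severity and type of any adverse event occurred before, through and after treatments", with no method of eliciting events.
- **Table 3 (Appendix I).** Safety Monitoring is marked at all six visits, with no method.

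The Primary Safety Endpoint section has two items: the expected immediate response, graded on the Table 4 scale, and a tally of recorded adverse events by number, type and severity.

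**The concern.** The second item of the primary safety endpoint counts events that get recorded, so it depends on how events are looked for. Effects that have cleared before a visit cannot be seen on the skin, and soreness may leave nothing to see at all. Such effects reach the CRF only if the subject mentions them or is asked. Table 2 has the subject asked; the other sections that describe a method do not say so.

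The study has one arm, so incomplete capture cannot cancel against a comparator and passes straight into the reported rate. With up to 10 sites, differing local practice could also add differences between sites that have nothing to do with the device. No section supplies a standard question or says which description governs.

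**Working it through.** There is no stated event rate, expected count or safety precision target to reproduce. The check is a comparison of the text, followed by an illustration on assumed inputs.

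**Step 1: the sections side by side**

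| Section | Skin examined | Subject asked | Other routes or limits |
|---|---|---|---|
| Table 2, Safety row | yes | yes | adverse-event form |
| Anticipated Adverse Effects | by observation | not mentioned | volunteered reports; device-related only |
| Return Visits | yes | not mentioned | adverse events nested under the skin item |
| Data Analysis, Safety | yes | not mentioned | all complications to be recorded |
| Post Treatment Procedures | yes (immediate response) | not mentioned | any adverse event to be recorded |
| Table 3 | method not stated | method not stated | every visit |

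Skin assessment does not conflict with Table 2, which also lists it. The gap is the missing interview.

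**Step 2: time available for an effect to clear** (windows from Table 3 and Return Visits)

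- Between treatments: 14 ± 5 days, so 9 to 19 days.
- Last treatment to first follow-up: 28 ± 7 days, so 21 to 35 days.
- Between follow-ups: nominally 28 days, and up to 28 + 7 + 7 = 42 days.

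The Risks section reports that earlier events were mild and resolved within the study period.

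**Step 3: one event traced through.** Take soreness that begins after Tx.3 and is gone by the 4-week follow-up. Under Table 2 the subject is asked, and it can be recorded. At a site working from Return Visits and Anticipated Adverse Effects, the skin shows nothing, and the event may be recorded only if the subject raises it.

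**Step 4: illustration on assumptions not in the documents.** Let p be the true share of subjects with an effect that clears between visits and v the chance that a subject mentions it unprompted. Interview is given 100% capture of these effects and observation 0%, which makes the gap as large as it can be.

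- Volunteered only: reported share = p × v. With p = 0.20 (24 of 120) and v = 0.3 to 0.7, this is 0.06 to 0.14, or 7.2 to 16.8 subjects.
- Half the subjects at interviewing sites: p × (0.5 + 0.5v) = 0.20 × 0.65 to 0.20 × 0.85 = 0.13 to 0.17.
- Over p = 0.10 to 0.30: reported share runs from 0.10 × 0.3 = 0.03 to 0.30 × 0.7 = 0.21. Shortfall p × (1 − v) runs from 0.10 × 0.3 = 0.03 to 0.30 × 0.7 = 0.21.
- For scale, the standard error √(p(1 − p)/120) is 0.027, 0.037 and 0.042 at p = 0.10, 0.20 and 0.30.
- For an uncommon event with a true rate of 1%, the chance of recording at least one case in 120 is 1 − 0.99^120 = 0.70 with full capture and 1 − 0.995^120 = 0.45 with half capture.

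**Step 5: does adding a question suffice?** The opening of the Adverse Events section defines an event as any adverse change in health during participation. The recording sentence under Anticipated Adverse Effects ends by limiting documentation to device-related signs and symptoms. A question about any change in health would therefore bring up events that this sentence then drops. It would also leave little use for the relationship category of not related, which the plan defines.

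**The case against.** The strongest reply is that the plan already requires the interview. Table 2 is introduced in mandatory terms and its Safety row applies throughout the study, so a site that never asks departs from the protocol and is not using a permitted alternative. The adverse-event section does not forbid asking. Other text narrows the gap:

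- Post Treatment Procedures asks for any adverse event, without a volunteered-or-observed condition.
- The Treatment Visit section collects pain scores.
- The safety analysis section covers all complications since study start.
- Dates of onset and resolution can hardly be filled in for a cleared event without asking the subject.
- Table 3 marks safety monitoring at every visit.

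All of this stands, and it rules out a reading that is tempting: that an event counts only if the subject volunteers it, or that the adverse-event section overrides Table 2. The documents say neither. The immediate-response item is also largely outside the concern, because staff grade it after each treatment.

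The reply does not remove the inconsistency. The follow-up list is what a site works through at the visits furthest apart, and it gives no instruction to ask. Nowhere is there a common question, so even sites that interview may do so differently.

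**Conclusion.** The plan describes adverse-event ascertainment inconsistently and does not reconcile the descriptions. It is not a strict contradiction, since interviewing every subject satisfies all sections. The likely direction of any effect is downward, on the adverse-event item of the primary safety endpoint, through effects that resolve between visits.

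The size cannot be derived from the documents. The 3 to 21 point range follows entirely from assumed event rates of 10% to 30%, assumed unprompted reporting of 30% to 70%, and perfect capture by interview. A reader might take it as an estimate of bias, or conclude that a pooled rate across sites has no clear meaning. Neither is supported: the plan sets no safety threshold, precision target or between-site comparison against which to judge it, and nothing shows that sites would in fact skip the interview. The point is worth correcting because the endpoint is primary, the study has no comparator, and the correction is cheap.

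**What to change.** Make the Table 2 interview the single rule.

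1. Ask one standard, non-leading question at every visit: whether there has been any change in health or in the treated area since the last visit. Add it to Post Treatment Procedures, Return Visits and the Safety Monitoring row of Table 3.
2. In Data Analysis, Safety, name subject interview alongside skin assessments.
3. In Anticipated Adverse Effects, widen the recording sentence to signs and symptoms that are volunteered, observed, or reported in answer to the standard question.
4. In that same sentence, remove the limit to device-related events. All events meeting the definition that opens the Adverse Events section are then recorded, and relatedness is classified afterwards with the plan's existing categories. The definition and the concurrent-illness sentence in the same paragraph carry a similar limit and should be aligned, or the change is undone.

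The cost is protocol wording and one CRF item, with no added visits or subjects. The reported adverse-event rate may be somewhat higher, and the report should say that events were actively elicited.
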